Sleep is directly impaired by opioids: There is a substantial preclinical and human literature demonstrating that opioids modify the sleep-wake cycle. Acute doses of opioids disrupt sleep in animal (Cronin, Keifer, Baghdoyan, & Lydic, 1995; Gauthier, Guzick, Brummett, Baghdoyan, & Lydic, 2011; Moreton, Roehrs, & Khazan, 1976; Watson, Lydic, & Baghdoyan, 2007) and human models (Dimsdale, Norman, DeJardin, & Wallace, 2007; Howe, Hegge, & Phillips, 1980; Kay, 1975a; Kay, Eisenstein, & Jasinski, 1969), and chronic opioid exposure produces persistent sleep disturbance in both animal (Robert, Stinus, & Limoge, 1999; Young, Moreton, Meltzer, & Khazan, 1975) and human (Dunn, Finan, Tompkins, & Strain, 2018; Kay, 1975b) models. In humans, chronic opioid use is associated with development of hypoxemia, sleep apnea (Charpentier, Bisac, Poirot, Vignau, & Cottencin, 2010; DeVido, Connery, & Hill, 2015; Farney et al., 2013; Mogri, Desai, Webster, Grant, & Mador, 2009; Peles, Schreiber, Hamburger, & Adelson, 2011b; Schwarzer, Aichinger-Hinterhofer, Maier, Vollert, & Walther, 2015; Wang et al., 2005) and disruptions in the hypothalamic-pituitary-adrenal (HPA) axis (Bunce et al., 2015) in a manner that impairs sleep. We know of only two studies that have empirically examined methods for improving sleep in OUD patients; these studies reported no benefit of electrostimulation or acute doses of methadone among patients being withdrawn from opioids (Gossop & Bradley, 1984) or the non-benzodiazepine trazodone in patients maintained on methadone (Stein et al., 2012b). Despite the lack of data, patients undergoing supervised withdrawal who experience sleep disturbance may first be prescribed hydroxyzine, then trazodone, and finally an antipsychotic such as quetiapine (Seroquel) (Pinkofsky et al., 2005).

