Screening Visits: Participants will be recruited from the community via flyers, newspaper postings, and other media outlets. Screening visits will take place on the Behavioral Pharmacology Research Unit at the Johns Hopkins Bayview Medical Center. Individuals will complete a phone-screen to assess for initial eligibility and will be invited for a clinic-based visit to confirm final eligibility. During this visit, participants will first review an informed consent form with a staff member and discuss the study before

providing voluntary informed consent to participate. Participants will then complete a series of measures to establish study eligibility, including a demographics questionnaire, self-reported opioid use and withdrawal, a past 30-day timeline follow back for drug and alcohol use, assessments of DSM-5 drug and alcohol use disorders, the Stop-Bang questionnaire assessment of sleep apnea, psychiatric functioning (MINI International Neuropsychiatric Interview [Sheehan et al., 1998]), and the Columbia Suicide Severity Rating Scale (Posner et al., 2011). Participants will provide a blood sample that will be tested for complete blood count and comprehensive metabolic panel, provide a urine sample that will be tested for evidence of opioid and other drug use, and pregnancy (when applicable). Either during the Screening or admission day, participants will complete a medical history and physical examination with qualified medical staff to determine final study eligibility. The physical examination will include an electrocardiogram (ECG) to determine if the participant has any heart abnormalities, and the Brief Pain Inventory to quantify current chronic pain issues (Cleeland et al., 1994). Opioid withdrawal scales will be collected at the end of the Screening visit to help confirm opioid physical dependence.

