Buprenorphine Induction and Stabilization: Participants will be inducted onto buprenorphine prior to beginning the buprenorphine taper. Induction may occur up to 3 weeks prior to admission to the CRU. Participants will be required to show evidence of opioid withdrawal (as per ratings on the COWS) and will receive incremental doses of buprenorphine throughout the day, up to a maximum of 16mg of buprenorphine on the induction day. The induction protocol will be conducted as clinically indicated, based upon medical team recommendations. To increase comfort during the induction, the medical team may administer the PRN concomitant medications that are approved for the taper protocol as well as clonidine. Participants may then be maintained on buprenorphine as an outpatient for up to 3 weeks before CRU admission. Briefly maintaining participants on buprenorphine will enable the study to retain participants between Screening and CRU admission, as the CRU has restricted access for protocols requiring weekend coverage. Participants who are maintained on buprenorphine as an outpatient will receive blister packages of sublingual buprenorphine for outpatient administration and may receive up to 24mg/day (beginning the day after induction) during this period. During the stabilization period between Screening and Admission, participants will be required to visit the clinic on a weekly basis to exchange blister packages. Participants may receive assistance (e.g., bus tokens) from the study to help facilitate transportation to the BPRU on those days. Any participant receiving >16 mg as an outpatient will be transitioned to 16mg on the CRU admission day. Participants who are inducted onto buprenorphine on the CRU admission day will follow an identical induction procedure and will only receive up to 16mg.

Clinical Research Unit (CRU): Following confirmation of eligibility, participants will be admitted onto a residential CRU that is located on the Bayview Medical Campus. Participants will reside on the CRU for up to 11 days (10 nights) and will be allowed to smoke cigarettes ad libitum in a designated smoking area during their stay. Female participants will provide a sample of blood upon admission that will be analyzed for levels of progesterone and estrogen.

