Brief Sleep Hygiene Education: During stabilization, staff will conduct a brief educational session with participants to provide information regarding appropriate sleep hygiene (Doshi et al., 2017). This session will ensure all participants have the same understanding of healthy sleep behaviors before the taper begins, to minimize the impact that differences in sleep hygiene has, and better isolate the impact of SUVO on study outcomes.

Overdose Education: During the stabilization period, participants will also complete a brief opioid overdose prevention computerized education session (developed by Co-I Dunn under NIDA R21DA035327).

Randomization to Group: Participants will be stratified into experimental group based on (a) baseline Pittsburgh Sleep Quality Index (PSQI) (<5/≥5), (b) peak SOWS ratings during buprenorphine induction (≤10/>10), (c) buprenorphine stabilization dose (<16mg/16mg), and (d) sex (M/F). Randomization will occur via a minimization procedure to balance the distribution of these characteristics

across the experimental groups. Study pharmacist staff, who have no direct participant contact, will oversee randomization and dispensing of study medications.

Taper Phase (4 days): Participants will undergo an open-label, step-wise buprenorphine taper. An open-label phase is necessary because buprenorphine placebo tablets/filmstrips are not available; however, this open-label design feature is of value because it increases the overall generalizability of the study results.

Post-taper Phase (4 days): Participants will continue study participation for four days (three nights) following buprenorphine discontinuation, to capture the full course of opioid withdrawal.

Study Medications: Double-blind study medication dosing will begin on the evening before Taper Day 1. Study medications will either be 20mg SUVO, 40MG SUVO, or placebo, which will be administered prior to bedtime. Though participants will be reminded to practice good sleep hygiene, no contingencies or consequences will be associated with their sleep behavior. This is because our extensive experience suggests that participants who are unable to sleep at night will attempt to sleep during the day; all sleep attempts will be captured by wrist actigraphy and nightly questionnaires and evaluated as outcome data. Placing contingencies on sleep parameters (such as no day-time sleeping) could also prompt attrition.

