- Have no clinically significant chronic medical or surgical disorders or conditions that are judged by the investigators to prevent participation.

Exclusion Criteria:

- Seeking or currently enrolled in methadone or buprenorphine maintenance treatment for OUD
- Pregnant or breast feeding.
- Have evidence of physical dependence on alcohol or benzodiazepines that requires medical detoxification.
- Have a known allergy to the study medications.
- Past 30-day prescribed use of suvorexant or benzodiazepines for the indication of insomnia.
- Current use of an SSRI or MAO inhibitor for depression or insomnia, or other medications that are contraindicated with suvorexant.
- Current narcolepsy, restless leg syndrome, or sleep paralysis.
- High risk for current sleep apnea as assessed via the Stop Bang questionnaire.
- Current major depressive disorder.
- Past year suicidal behavior as assessed via the Columbia Suicide Severity Rating Scale
- Severe hepatic or renal impairment, defined as:
 - AST or ALT $>3x$ ULN.
 - Total Bilirubin $>2x$ ULN.
 - Creatinine $>1.5x$ ULN.
- Have circumstances that would interfere with study participation (e.g., impending jail).

6. Drugs/ Substances/ Devices

- a. The rationale for choosing the drug and dose or for choosing the device to be used.

Suvorexant (SUVO): SUVO is FDA-approved for the treatment of insomnia and is an ideal candidate for evaluation because it is intended for PRN administration, improves sleep architecture after a single dose (Herring et al., 2016b; Sun et al., 2013), and does not cause a withdrawal syndrome after abrupt discontinuation even when it has been administered chronically for several weeks (Herring et al., 2016b). This study utilizes two doses of SUVO (20 and 40mg) to evaluate which dose has a superior risk/benefit profile, although we do not anticipate a high rate of adverse events for either dose. The most effective dose can then be used in future clinical trials as well as in practice for the treatment of sleep disturbance during opioid withdrawal. Participants will be given their medication dose in two weight and color-matched capsules, containing either two 20mg SUVO (40mg dose), two 10mg SUVO (20mg dose), or two placebo capsules. As an added precaution, participants will be allowed to reduce their dose from two to one capsule (representing a 50% dose decrease) if they experience negative side-effects and would prefer a lower dose.

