1. Risk associated with suvorexant (Belsomra®): Suvorexant is a Schedule IV dual orexin antagonist that is FDA-approved for the treatment of insomnia. Suvorexant is 82% bioavailable and has a Tmax of 2 hours. Tmax can be delayed by food though this does not impact the Cmax. It is extensively metabolized by the liver through CYP3A enzymes. The elimination half-life is 12 hours, and it is excreted through both renal (23% unchanged) and fecal (66%) means. Suvorexant is contraindicated with other CNS depressants and alcohol and strong CYP3A inhibitors. It is rated pregnancy category C, indicating insufficient data available to make determination for human subjects. Suvorexant is contraindicated in patients with narcolepsy, patients with recent suicidal behavior, or patients with severe hepatic impairment. There is no evidence of potential overdose and a toxic dose has not been established. Clinical trials that administered up to 240mg of suvorexant reported no overdose effects, though there was a dose-dependent increase in the frequency and duration of next day somnolence. As per product label, most common side effects are sleepiness/drowsiness (7% of people), headache (7%), dizziness (3%), diarrhea (2%), dry mouth (2%), upper respiratory infection (2%), abnormal dreams (2%), and cough (2%). Serious adverse effects include sleep paralysis (7%), somnolence (7%), and worsening of depression or suicidal ideation.

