2. Risks associated with buprenorphine/naloxone: Participants in this study will be maintained on buprenorphine/ naloxone briefly before beginning a 4-day buprenorphine/naloxone taper. Buprenorphine is Schedule III FDA-approved medication that is approved for the indication of opioid withdrawal treatment. Participants in this study will receive the generic sublingual tablet version of this product (which also has naloxone). Buprenorphine is partial opioid agonist/antagonist at the opioid mu/kappa receptors (respectively), has a low ceiling on its agonist effects, and a slow dissociation from the receptors that results in a 26-hour elimination half-life. There is nothing experimental about the use of buprenorphine/naloxone use in this study. All participants will receive the same buprenorphine/naloxone detoxification schedule, and the highest potential dose (24mg) is well below what can be administered for use on a daily basis (32mg). Buprenorphine/naloxone has very few contraindications, and is not recommended for patients with respiratory distress (such as acute or severe bronchial asthma, or respiratory depression), patients with a known allergy to buprenorphine, or patients with history of cardiac problems such as long QT syndrome or severe hypotension. It is contraindicated for use with the opioid antagonist naltrexone or other opioid agonists. It is rated in pregnancy category C, therefore all women who are pregnant or breastfeeding will be excluded from study participation. Buprenorphine/naloxone's noted side effects are minimal and rare (hyperhidrosis 14%, abdominal pain 11%, constipation 12%, nausea 15%, headache 37%, insomnia 14%) and overlap significantly with known opioid withdrawal symptoms (e.g., abdominal pain, nausea).

3. Risk associated with opioid withdrawal: It is expected that participants will experience some level of opioid withdrawal as part of this study. Symptoms of opioid withdrawal include nausea, diarrhea or stomach cramping, muscle aches and pains, yawning, sweating, pupil dilation, minor increases in blood pressure, and runny nose/tearing eyes.

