Adverse events will be assessed daily. The safety of participants is a priority of our research unit. The largest potential risks to participants on SUVO are worsening of depression and/or sleep paralysis. We will exclude any participant with current major depressive disorder, past year suicidal behavior, or self-reports of current sleep paralysis. Medical team members will be consulted about adverse events and we will follow all reporting guidelines. In the event of an SAE, appropriate courses of action may include observing the participant until the parameters return to normal or transferring the participant to the Emergency Department (ED). Our research unit, the location in which all study sessions will be conducted, is located across the street from the Johns Hopkins Bayview Medical Center (JHBMC) ED. Participants who can walk will be escorted to the ED by a study staff member. If there is any question in a participant's ability to walk safely then 911 will be called to have an ambulance dispatched for the participant.

Given the small sample size, the relatively short study duration, and the fact that medications are being administered as clinically-indicated, we are not planning an interim analysis.

c. Plan for reporting unanticipated problems or study deviations.

Adverse events may be identified by a member of the research staff, the Principal Investigators, or study co-investigators. The PI will be responsible for consulting a medical team member about adverse events. The PI and research staff will meet on a weekly basis to review safety monitoring data and adverse events and to ensure that any safety concern has been addressed by medical staff and has been recorded appropriately.

All SAEs will be reported to the JHM IRB within 3 working days after a study PI learns of the event. In addition, the study PI will notify the study co-investigators, the NIDA Program Official, and the FDA (if applicable). The PI will coordinate dissemination of subsequent information obtained relating to the death (e.g., autopsy report, hospital records, toxicological analyses).

The Johns Hopkins IRB will be provided with an annual summary of AEs and SAEs as part of the continuing review. If any SAEs requires a change to the protocol or consent form, the PI will make those changes promptly and submit the revised documents to the JHM IRB and appropriate other agencies.

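### Bedtime suvorexant is given on top of a buprenorphine taper that the protocol's own contraindication sentence seems to cover, with no discussion of the pair and no rule for withholding a single dose

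*Combined protocol and SAP*

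**What the plan says.** On the drug pair:

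- Section 8.a, suvorexant item: "Suvorexant is contraindicated with other CNS depressants and alcohol and strong CYP3A inhibitors". No exception is made for study medication.
- Section 5 excludes current use of an SSRI or MAO inhibitor "or other medications that are contraindicated with suvorexant".
- Section 4.a, Study Medications: "Double-blind study medication dosing will begin on the evening before Taper Day 1". Section 6.a describes a 3-day stabilization, for example at 8-16 mg/day of buprenorphine, followed by a 4-day taper.
- Section 6.b gives 10 and 20 mg as the approved suvorexant doses, so the 40 mg arm is above them.
- Section 8.a, buprenorphine item, describes a partial mu agonist with a low ceiling to its agonist action and a 26-hour half-life. It advises against use in respiratory depression.

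On monitoring and action:

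- Vital Signs (Study Measures, section 4.a) include respiration and oxygen saturation several times daily. No clock times or action limits are given.
- Section 6.a lets a participant who has side effects choose to halve the dose. Sections 4.f and 7.d allow removal from the study on request, after a serious adverse event or on medical judgement.
- Section 8.b: "The largest potential risks to participants on SUVO are worsening of depression and/or sleep paralysis".
- Section 8.a, clonidine item, bars that drug when blood pressure is below 80/60.

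**The concern.** Section 8.a lists risks one drug at a time, so the combination that defines the active arms is never addressed. The Background gives a reason to address it: in humans, "chronic opioid use is associated with development of hypoxemia, sleep apnea". The reassuring respiratory data for suvorexant in section 3 are not described as collected in people taking an opioid, and the same section says suvorexant had not been studied in patients with opioid use disorder.

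The practical gap is the single dose. The protocol collects saturation and respiration but does not say what reading means that tonight's capsules are not given. At stake is whether someone already desaturated, breathing slowly or hard to rouse at bedtime is reliably spared a further 20 or 40 mg. Section 6.a also intends to compare the two doses on risk and benefit, and readings taken at a fixed point before each dose would inform that comparison.

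**Working it through.** The plan states no figure on this point, so the check is a side-by-side reading plus a count of exposure.

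**1. Is any dose subject to a written hold?**

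| Provision | What triggers it | What it does |
|---|---|---|
| Halving the dose (6.a) | Side effects and participant preference | Reduces the dose |
| Removal (4.f, 7.d) | Request, serious adverse event, medical judgement | Ends participation |
| Vital signs (4.a) | None stated | Recorded several times daily |
| Stop-Bang exclusion (5) | High apnea risk at screening | Excludes before entry |
| Clonidine limit (8.a) | Blood pressure below 80/60 | Drug not given |

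Only the clonidine row is a written hold, for a drug the protocol expects to use in very few participants. Suvorexant has none.

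**2. Planned same-day doses.** Inputs: 15 per arm (section 7.c), two active arms, first dose on the evening before Taper Day 1, 4-day taper. The taper steps are not given, so whether the last taper day carries buprenorphine is unknown.

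- Without buprenorphine on Taper Day 4: 1 + 3 = 4 doses each, 30 x 4 = 120, of which 15 x 4 = 60 at 40 mg.
- With it: 1 + 4 = 5 doses each, 30 x 5 = 150, of which 15 x 5 = 75 at 40 mg.

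Both totals assume that everyone completes.

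**3. Overlap after the last buprenorphine dose.** With first-order decay, the fraction left is 0.5^(t/26):

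- 24 h: 0.5^(24/26) = 0.53
- 48 h: 0.5^(48/26) = 0.28
- 72 h: 0.5^(72/26) = 0.15

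The same-day count is therefore not an upper bound on overlap. These figures describe exposure and carry no event rate.

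**4. Number of checks.** The evening before Taper Day 1, four taper nights and three post-taper nights make 8. The analysis section counts 7. So 45 x 7 = 315 to 45 x 8 = 360 checks.

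**5. What held doses could cost in power.** The protocol gives no basis for a hold rate. As an illustration only, assume 1% to 5% of checks trigger:

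- All arms: 315 x 0.01 = 3.2 to 360 x 0.05 = 18 doses.
- Active arms: 210 x 0.01 = 2.1 to 240 x 0.05 = 12 doses.

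For power, read the stated 0.70 as Cohen's f in a three-group ANOVA with N = 36 and alpha 0.05. The metric and alpha are my assumptions. Noncentrality is f² x 36 on 2 and 33 degrees of freedom. If the effect shrinks in proportion to the doses held:

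| Held | f | f² x 36 | Power |
|---|---|---|---|
| 0% | 0.700 | 17.64 | 95.7% (plan: 95%) |
| 1% | 0.693 | 17.29 | 95.4% |
| 5% | 0.665 | 15.92 | 93.7% |

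Uniform shrinkage is a simplification, because holds could cluster at 40 mg.

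**The case against.** The best defence is that care is already in place. Participants live on a unit with nursing staff, adverse events are assessed daily with medical consultation, added sleep aids and clonidine are barred after randomization, high apnea risk is excluded, and an IND is to be requested. The suvorexant item itself lists somnolence and its dose dependence, and section 8.b speaks of the largest risks, not the only ones. A physician can hold a dose without a written rule. All of this stands, and it limits the point to a missing written criterion.

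Three stronger readings do not stand.

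- A reader might infer that section 5 bars study buprenorphine and so makes everyone ineligible. That is strained: buprenorphine is mandatory, and maintenance treatment has its own exclusion. The wording needs only a clarification.
- A reader might infer that the trial breaches a product-label contraindication. The protocol never classes buprenorphine as a CNS depressant; that step is general pharmacology. Whether the sentence matches the label cannot be checked here.
- A reader might infer that participants go unwatched or that respiratory harm is expected. The monitoring provisions contradict the first, and no event rate supports the second. One reference title, on sleep-disordered breathing decreasing after opioid withdrawal, points the other way for a tapering population.

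Two objections to a hold rule also have force. A check in someone awake cannot see breathing during sleep. And a trigger based on sleepiness would be loose for a hypnotic and could fire more often at 40 mg, hinting at allocation and leaving no dose behind the next morning's Drug Liking rating, a primary outcome. The trigger must therefore be narrow.

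**Conclusion.** The point holds as a cheap safety improvement, with medium confidence. The protocol states a contraindication, plans 120 to 150 doses that appear to fall under it, discusses the pair nowhere and links no reading to withholding a dose. The dose count rests on full enrolment and completion and on the unstated last taper step. Treating buprenorphine as a CNS depressant rests on general pharmacology, supported by the protocol's own caution about respiratory depression. The finding does not show that participants would be harmed, and it does not affect the validity of the efficacy comparison. The dose hold is the part that changes what the trial does; the wording changes alone would be documentation.

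**What to change.** 1. **Pre-dose check and hold.** Take one of the planned saturation and respiration readings, with a brief arousability check, just before each bedtime dose. Withhold that night's dose, in any arm, if a limit set by the study physicians and written in the protocol is crossed. Triggers should be low saturation, slow breathing or difficulty in rousing, not ordinary bedtime sleepiness.
2. **Analysis.** Record held doses, analyse participants as randomised, and flag the next-morning Drug Liking rating after a held dose. Report pre-dose readings by arm.
3. **Wording.** In section 8.a amend only the CNS-depressant clause, to say that co-administration with protocol-supplied buprenorphine is planned and monitored, and add a short paragraph on the combined risk. Keep the alcohol and strong CYP3A inhibitor contraindications. In section 5 state that study buprenorphine is exempt.

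**Cost.** A small amendment and 315 to 360 timed checks by staff already on the unit, with no new device and no change to arms or sample size. Because the vital-signs schedule gives no clock times, a reading may have to be moved to bedtime; the arousability check is new. An unknown number of doses would be held, possibly more at 40 mg, with slight dilution of the effect. A common rule lessens the threat to the blind but does not remove it.
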